17.1 Early termination and close of recruitment

The study has to be terminated immediately, if a SAE with probable association to the study therapy occurs in more than 2 out of the first six patients or more than four out of the first 10 patients or in more than 40% of all recruited patients thereafter. The study may be terminated on the decision of the principal investigator in case of the following events:

- Insufficient recruitment
- new scientific data which either definitively answer the scientific question or require major changes of the protocol which cannot be included in an amendment

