- age ≥ 18 years
- Legal capacity, patient is able to understand the nature, significance and consequences of the trial
- Written informed consent

Exclusion criteria:

- Relevant comorbidity (with limitations to administer radiotherapy according to protocol)
- Prior radiotherapy which results in limitations to administer radiotherapy according to protocol
- No large metal implants in vicinity of lesion
- Department dose constraints for normal tissue can't be met
- Large bony lesions with extensive osseous destruction (e.g. vertebral body)
- Patients symptoms do not correlate with MR findings

7 Risks and toxicities

Patients participating in this study will have standard radiotherapy. Consequently, the participating patients face known risks and toxicities following high dose radiotherapy. Patients participating in this study are offered a higher than normal radiation dose to their dominant lesion, but treatment plans will adhere to department standard dose constraints for all organs at risk in order to avoid excessive risks and toxicities.

8 Registration

The consecutive cohort of HRPC patients will be screened for eligibility according to the inclusion criteria's in this protocol. Estimated median survival for patients to be included should preferably be based on the updated model in (6) (see appendix 1). Before inclusion, patient clinical routine blood lab and radiology results should be reviewed. Available clinical routine diagnostic imaging and lab results may be used to calculate the expected median survival for patients using the model in (6) (see appendix 1). (6)Eligible patients will be informed about the study. After given informed consent, patients may be included in the

study. All patients included in the study receive a patient identification number (PID). The PID is composed of the site number and the running patient number (starting with P01, P02,.. ect.).

Site	SiteID
Naestved, Denmark	C1
Kiel, Germany	C2
Lübeck, Germany	C3

For **pseudonymous** registration and recording of all protocol data, the department of oncology, Naestved, will be make an electronic web interface (Easytrial) available for participating sites.

9 Systemic therapy

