10.3 Target volumes

Patients included in the study will be subjected to a protocol-specific MRI examination (see MR sequence and example of target delineation in appendix 19-20). A radiologist will read the MRI scan to validate correspondence between MR lesion and the patients dominating symptoms. In case of more than one lesion, decision on priority of target volumes will be made by the radiation oncologist based on clinical expertise. An ADC map will be calculated for the lesion using the DWI sequences. A cutoff ADC value of less than 1200×10^{-6} mm²/s in combination with a T2w image will be used to predict the MR lesion (GTV1) (26). The most aggressive part of the lesion (GTV2) will be defined using ADC of less than or equal to a cutoff value calculated as the median ADC value for the GTV1 (25). Notice that GTV2 need not to be one coherent volume, but may consist of several sub-volumes.

For the definition of target volumes, the following aspects should be considered: The clinical target volume (CTV) is the visible macroscopic tumor (GTV). The safety margin for the planning target volume (PTV) should be according to the department standard, and depending on the radiation technique used. The margin for the PTV2 for CTV2 may be chosen to be smaller than for PTV1 as this volume is enclosed in the CTV1, which receives a dose of 4 x 5Gy already.. For the treatment of breathing-dependent lesions (upper abdomen), treatment techniques with motion compensation (e.g. breath-hold or gating) should be used. All four fractions of the treatment should be given within two weeks of starting the radiotherapy.

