10.6 Start of radiotherapy

Radiotherapy should be started within three weeks after inclusion of the patient in the study.

11 Trial Procedures and Assessment

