12.1 Adverse events

An adverse event (AE) is defined as any event experienced by a patient or subject of a clinical trial, which does not necessarily have a causal relationship to the study treatment.

The severity of AEs should be assessed by using the National Cancer Institute Common Terminology Criteria for Adverse Events (CTCAE version 4.03). If an AE occurs, which is not described in the CTCAE version 4.03, the following five-point scale should be used for assessment: grade 1 = mild, grade 2 = moderate, grade 3 = severe, grade 4 = life-threatening and grade 5 = fatal.

The investigator must also systematically assess the causal relationship of the AEs to the trial treatment. The AEs should therefore be classified as reasonably related or not reasonably related (unrelated) to trial treatment.

- All AEs experienced will be documented in the appropriate section of the CRF.
- Any clinical AE with severity of grade 4 or 5 must also be reported as an SAE.

Severe adverse events (SAE)

A severe adverse event (SAE) is any untoward medical occurrence that meets the following criteria:

- Results in death.
- Is life-threatening
- Requires hospitalization or prolongs an existing hospitalization.
- Results in persistent or significant disability
- Is a congenital anomaly or birth defect.
- Is otherwise considered medically important.

All SAEs must be documented and reported to the sponsor within 24 hours after awareness of the event using the online web interface for Easytrial.

13 Data and Safety Monitoring Board

Data will be entered pseudonymously into an online web based electronic database, Easytrial, and data stored on servers in Denmark. Access to the web interface is by invitation via email to staff participating in the study only. The Data and Safety Monitoring Board (DSMB) reviews safety after the first ten and after the

last patient have been treated and the respective data validated and tabulated. It may recommend restrictions to treatment regimens and patient eligibility.

14 Endpoint Adjudication Committee

The Endpoint Adjudication Committee (EAC) receives pseudonymized MRI scans and the Radiotherapy treatment plan for all patients up to end of trial. The EAC will assess when progression free survival ended.

15 Quality Assurance

The Monitoring at the German sites according to GCP is performed by ZKS Kiel/Luebeck.

The Danish sites will be monitored according to the Danish regulations in their own responsibility.

16 Statistical aspects

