16.1 Case number

The objective of this study is to investigate the feasibility of applying hypo-fractionated radiotherapy to treat a dominant symptomatic lesion in patients with HRPC. The hypothesis is that at least 90% of the recruited patients complete combined systemic and local treatment with at least 90% of scheduled radiation dose administered. We use a two-sided one-sample proportion score test to compare the proportion of feasible cases to a reference value of 90%. We want to detect any difference with statistical significance of 5% and a power of 80% for not overlooking a true proportion non-feasible of 70%. The necessary sample size is estimated to 24 cases. Drop-out may happen either due to exclusion, or because patients withdraw their consent for participation. For patients with poor prognosis a realistic drop-out rate is estimated to be 30%, which implicated that **34 patients** must be included in the study to reach significance.

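### The 40% stopping limit counts therapy-related SAEs against all recruited patients, so every recruit who is not irradiated raises the limit that applies to treated patients

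*Protocol*

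**What the plan says.** Section 17.1 sets a mandatory stop with three limbs, all counting patients with an "SAE with probable association to the study therapy". The first limb is more than 2 of the first six patients and the second is more than four of the first 10. The third is "in more than 40% of all recruited patients thereafter". The first two limbs say only patients; the third says recruited.

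Other sections determine who can be recruited without being irradiated:

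- **Section 10.3:** "Patients included in the study will be subjected to a protocol-specific MRI examination". The flowchart in Appendix 4 also places consent and inclusion before the MRI.
- **Section 6:** the exclusion criteria include "Patients symptoms do not correlate with MR findings" and "Department dose constraints for normal tissue can't be met".
- **Section 10.6:** "Radiotherapy should be started within three weeks after inclusion of the patient in the study".
- **Section 16.1:** "a realistic drop-out rate is estimated to be 30" per cent, with exclusion and withdrawal of consent as the named causes.

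Section 13 uses a different basis. It times the DSMB safety reviews after the first ten patients and after the "last patient have been treated and the respective data validated and tabulated".

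**The concern.** The study therapy is the radiotherapy. A patient who has received none cannot contribute to the numerator of the third limb but does contribute to its denominator, so each such patient dilutes the observed rate and delays the stop.

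The protocol gives reasons to expect such patients. Agreement between symptom and lesion is judged on an MRI done after inclusion. Dose constraints can be checked only once a plan exists on the MRI-defined targets. Radiotherapy may start up to three weeks after inclusion, and drop-out is planned for.

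After patient 10 this limb is the only trial-level safety threshold. The DSMB has no scheduled review between the tenth and the last treated patient. SAE reporting within 24 hours (Section 12.1) and withdrawal of individual patients (Section 17.2) continue, but neither sets a limit for the trial. The patients concerned receive a higher than usual dose to the lesion (Section 7).

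A smaller point sits in the same sentence. The rule counts SAEs of probable association, while Section 12.1 records causality only as reasonably related or not. The numerator is therefore not defined in terms of the recorded data, although this does not in itself delay a stop.

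**Working it through.** **Inputs.** Limit 40% of recruited patients (17.1); 34 recruited (Synopsis, 16.1); drop-out 30% (16.1); recruitment over 12 months (16.2); wait of up to three weeks (10.6). The untreated share u is not stated, so I assume a range of 0 to 30%. The top value means that all planned drop-out occurs before the first fraction.

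**The plan's own figures.** The two-sided score test of 90% against 70% with 5% significance and 80% power gives n = [(1.96·√(0.9·0.1) + 0.842·√(0.7·0.3))/0.2]² = 23.7, so 24. Then 24/0.70 = 34.3, stated as 34. The 40% limit has no derivation to reproduce.

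**Effective limit.** Let R be recruited, T = (1-u)R irradiated, and X the patients with a therapy-associated SAE, all of them among T. Then X/R > 0.40 is the same as X/T > 0.40/(1-u). At R = 34 the rule as written needs floor(0.4·34)+1 = 14 affected patients; on a treated basis it needs floor(0.4·T)+1.

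| u | T | Limit among treated | Needed, as written | Needed, treated basis |
|---|---|---|---|---|
| 0% | 34 | 40% | 14 | 14 |
| 6% | 32 | 43% | 14 | 13 |
| 10% | 31 | 44% | 14 | 13 |
| 20% | 27 | 50% | 14 | 11 |
| 30% | 24 | 57% | 14 | 10 |

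In whole patients, 14 of 24 is 58.3%.

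**The wait alone.** With even accrual and a full three-week wait, 34/52·3 = 2.0 recruits are waiting at any time, which is 6% of 34. Early on they weigh more: 0.40/(1-2/11) = 48.9% at 11 recruited, against 44.4% at 20 and 42.9% at 30.

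**Meaning of thereafter.** If it covers only patients recruited after the tenth, the formula is unchanged. With 24 such recruits and 17 irradiated (u about 30%), the trigger is 10, and 10/17 = 58.8%.

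**Chance of stopping.** I simulated 400,000 trials per setting. Each of 34 recruits is untreated with probability u, SAE status is known at once, counts run from the first patient, and the limit is checked after every patient from the eleventh. Ranges reflect whether the treated-basis check begins at the eleventh recruited or the eleventh treated patient.

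Third limb alone, recruited against treated denominator:

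| u | True rate 50% | True rate 30% |
|---|---|---|
| 0% | 96% vs 96% | 38% vs 38% |
| 6% | 92% vs 95% | 32% vs 38% |
| 10% | 89% vs 95% | 27% vs 38-39% |
| 20% | 76% vs 94% | 18% vs 37-41% |
| 30% | 58% vs 92-93% | 11% vs 36-43% |

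Whole rule, if the first two limbs already count treated patients:

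| u | True rate 50% | True rate 30% |
|---|---|---|
| 10% | 91% vs 96% | 37% vs 44% |
| 20% | 84% vs 95% | 32% vs 43% |
| 30% | 78% vs 93% | 30% vs 42% |

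If the first two limbs also count recruited patients, whole-rule stopping as written at a 50% rate is 90%, 79% and 63% at u = 10%, 20% and 30%.

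**The case against.** The strongest reply is that u may be small. The Synopsis says that meeting any exclusion criterion rules out recruitment, so a patient with an MRI mismatch or unmet dose constraints might never count as recruited. The trial's own hypothesis is that at least 90% of recruits complete treatment, which would leave at most 10% never irradiated. Consent can also be withdrawn after irradiation. This stands in part: 30% is an extreme, and the figures at 10% or below are more plausible if the trial goes as hoped. It does not remove the point. Section 10.3 and the flowchart put the MRI after inclusion, Section 16.1 lists exclusion as a cause of drop-out, and patients who are waiting or withdraw before treatment remain in the denominator on any reading.

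Second, the third limb never acts alone. The first two limbs, counted on treated patients, stop about 73% of trials at a true rate of 50%. The whole-rule figures are therefore the fair measure, and they show a smaller loss.

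Third, the change is a trade-off. At u = 10%, whole-rule stopping rises by 4.3 points at a 50% rate (91.2% to 95.5%) but by 7.1 points at a 30% rate (37.0% to 44.1%). That is true. It returns the rule to about the 44% it gives at a 30% rate when every recruit is treated, so the extra stops belong to the 40% limit the protocol chose.

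Fourth, recently treated patients whose SAEs have not yet appeared dilute a treated denominator too. That also stands, and the proposed change does not cure it.

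**Conclusion.** The concern holds. As written, the third limb tolerates a therapy-related SAE rate among irradiated patients of 40%/(1-u), above the stated 40% whenever any recruit is unirradiated. That is an identity and needs no assumption. Its size depends on u, which the protocol does not give: nil at 0%, a limit of 43% from the three-week wait alone, 44% at u = 10%, and 57% in the upper case of 30%. For the whole rule at a true rate of 50%, the loss in stopping probability runs from about 4 points (u = 10%) to about 15 points (u = 30%), assuming that the first two limbs count treated patients, that counts are cumulative and that SAEs are known at once. The effect is modest if few recruits go untreated, but this is a binding safety rule and should apply the limit it states.

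**What to change.** In Section 17.1, define the denominator of all three limbs as patients who have received at least one fraction of study radiotherapy, and the numerator as those of them with an SAE classified as reasonably related under Section 12.1. The same sentence should say whether the third limb counts from the first patient. If the sponsor and DSMB want a tolerance above 40% among treated patients, they should state that percentage openly.

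This costs one sentence and leaves the sample size unchanged. The price is earlier stopping, including when the true rate is below 40%. At a 30% rate, whole-rule stopping rises from 37% to 44% at u = 10%, from 32% to 43% at 20%, and from 30% to 42% at 30%.

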17.2 Study termination in individual patients

Participation in the study and study specific therapy must be stopped at any time during the study in individual patients for any of the following reasons

- withdrawal of informed consent by the patient
- severe toxicity with limitations or unacceptable risks to administer further study therapy
- inter current disease with limitations to administer protocol therapy
- progression of disease

[figure not shown]
18 Ethical and legal aspects

The study will be conducted according to the declaration of Helsinki. Approval by the ethical committees of the participating institution is required prior to initiation of the study. Patients must be fully informed about the study and give informed consent prior to inclusion. National rules for data protection must be obeyed.

The study concept has been evaluated by the expert panel of DEGRO (German Association of Radiation Oncology). Approval by the German Radiation Protection Authority (BfS) is not required. A patient insurance will be taken out before the start of the trial for all patients, if necessary according to national rules. The trial will be registered in a primary study register before the start of the study.

This study receive financial support from EU via the Interreg project.

19 Appendix 1 – Calculation of median survival

20 Appendix 2 – Diagnostic MR Protocol sequences

MR protocols are modified/adapted from (24) and (27) to cover the lesion that explains the dominant symptom.

The MR sequence protocol must contain an anatomical (T2w) axial sequence (reference scan see table below), that can be co-registered to the planning CT, ie. the reference scan must include enough rigid anatomical structures for a co-registration with good accuracy. The remaining MR sequences must cover the dominant lesion with adequate margin (typically 50 mm) that will allow for outline of the lesion in 3D. All MR sequences must be acquired with the same dicom origo, ie neither, the patient nor, the dicom origo may be moved between sequence acquisitions. This will allow all MR images to be co-registered to the planning CT.

Sequence	Directions	Slice mm	TR msec	TE msec	Avg
T2-weighted fast SE	Ax* / Cor / Sag	3/ 5/ 5	2850	80	4
T1-weighted GRE SPIR**	Ax	5	1000	3.7	4
Proton density-weighted fast SE	Ax	5	2850	4.7	4
DW imaging*** with free-breathing SE EPI SPIR*	Ax	5	4687	64	8

Avg = number of sample averages

* Reference scan = T2w axial images

[figure not shown]
** SPIR = Spectral Presaturation with Inversion Recovery

*** b0 images and three b-values: b=50, 500 og 900 sec²/mm

[figure not shown]
Fat suppression should be preferably be done with a selective method as SPIR if possible. If not the STIR method, less specific, alternative method to use. Some post processing of MR images may be necessary to suppress noise in the images before automatically outlining the GTV. The ADC map should be calculated using all three b-values and mono-exponential fitting.

21 Appendix 3 - Target outline procedure

[figure not shown]
The following example demonstrate the target outline procedure on the MR images. This example is a reconstruction based on images from (28)

The target is outlined on the T2W image. This image is co-registered to the ADC map and the outline is transferred to the ADC map.

The outline transferred to the ADC map is subsequently corrected using a threshold for the $ADC < 1200 \text{ mm}^2/\text{s}$ for the target. This target is named GTV1

The median ADC value for the GTV1 target. The median value is used as threshold to obtain the most aggressive part of the target. This subvolume is named GTV2.

22 Appendix 4 – Flowchart for the study

	Inclusion	Visit 1 Baseline before RT	After RT	Visit 2 1 month	Visit 3 3 month	Visit 4 6 month
Screening / Inclusion	X					
Informed Consent	X					
Medical history	X					
MR scanning		X		X		X
Anamnesis		X				
Medical examination		X	X	X	X	X
Local Symptoms		X	X	X	X	X
Quality of Life		X				X
Toxicity		X	X	X	X	X
LPFS			X	X	X	X
ADC Response			X			X
Survival			X	X	X	X
AE/SAE			X	X	X	X
Concomitant medication		X	X	X	X	X
VAS		X	X	X	X	X
ECOG		X	X	X	X	X

23 References:

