Exclusion criteria (recruitment is not possible if any -at least one- criterion is met)	
 • Relevant comorbidity (with limitations to administer radiotherapy according to protocol) • Prior radiotherapy which results in limitations to administer radiotherapy according to protocol • No large metal implants in vicinity of lesion • Department dose constraints for normal tissue can't be met • Large bony lesions with extensive osseous destruction • Patients symptoms do not correlate with MR findings
Study therapy	
 • Image guided radiotherapy (IGRT) with hypo-fractionated simultaneous integrated boost (IMRT) • GTV1 = MR T2w lesion and ADC $\leq 1200 * 10^{-3}$ mm2/s • GTV2 = MR T2w lesion and ADC \leq median ADC in GTV1 • Each lesion is a CTV, CTV = GTV • PTV=CTV+ margin according to department standards • Dose-fractionation • CTV1: 4 x 5 Gy • CTV2: 4 x 7 Gy
Primary endpoint	Feasibility: Proportion of study participants that complete radiotherapy with $\geq 90\%$ of prescribed dose
Secondary endpoints	
 • Dominant symptom (VAS) • Progression-free survival >6 months • Overall survival

	
• Acute toxicity• Quality of life• Change in ADC from before to end of treatment• Change in ADC from before to 6 month post treatment
Sample size	34 patients has to be included in the study
Study sites	University Hospital Sjaelland, Naestved UKSH Campus Kiel UKSH Campus Luebeck
Time table	Recruitment period: 12 months Start of study: March 2018 End of study: March 2019 Follow-up: minimum \geq 6 months
Financing	Interreg (InnoCan)

3 Background and rationale

Prostate cancer is the major cause of cancer death in men living in developed countries. Large autopsy studies found that patients that presented prostate cancer demonstrated metastatic disease in 35% of cases. Prostate cancer metastases were 90% bone metastases, with 90% of the bone metastases involved the spinal cord, followed by lung (46%), liver (25%) and pleura (21%). Another important pathway is the lymphatic system, which is involved in 9 to 16% of cases, especially at the level of obturator, pre-sacral, internal, and common iliac arteries, and sometimes even the extra-regional para-aortic chains (1).

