10.1 General remarks

The primary endpoint is feasibility. The secondary endpoints are duration of relief from local symptoms, i.e. local symptom progression free survival (LPFS), overall survival, treatment toxicity (RTOG/CTCAE 4.0), Quality of life (EORTC-QLQ-C30 and EPIC26), and change in ADC as surrogate marker of response (21-25). Patients are scheduled for protocol specific follow-up visits at 1, 3, 6 months after end of radiotherapy. Additional MRI (T2w and DWI) will be performed at 1 and 6 months after end of radiotherapy or in case of progression of the dominant symptom.

Preferred technique is hypo-fractionated with high precision radiotherapy (radiosurgery or stereotactic radiotherapy) with few (1 to 5) fractions and ablative total dose. Daily IGRT is mandatory for hypo-fractionated regimens. For the treatment of thoracic lesions and metastases in the upper abdomen, techniques for motion compensation (e.g. breath-hold- or gating techniques) should be used, if available. In specific situations (e.g. spinal metastases with involvement of the spinal canal or cord compression or metastases with infiltration of hollow organs), however, lower doses of radiotherapy may be necessary for adherence of dose constraints or to avoid radiation-induced complications such as perforation. In these cases, moderately hypo-fractionated or even conventionally fractionated regimens should be used. The total dose should exceed at least a dose equivalent to 50Gy in conventional fractionation.

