11.4 Follow-up visits

Protocol visits are required at registration for the trial and at end of radiotherapy and at 1,3 and 6 months after end of treatment (see flowchart in appendix 3). At this time, the following examination will be performed:

- Review of concomitant medication, analgesia, opioids, current systemic anti-cancer treatment
- Review of clinical routine blood and radiology results
- Dominant symptom score (VAS)
- Acute toxicities of radiotherapy , RTOG/NCI score
- Quality of life (EORTC-QLQ C30) (only at 6 months)
- ECOG performance status
- Assessment of AE/SAE

All later visits are scheduled according to standard guidelines and institutional procedures.

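### Section 17.2 ends participation, not only therapy, at disease progression, which conflicts with the visits, quality of life, survival and safety data that the protocol requires to month 6

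*Protocol*

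**What the plan says.** Protocol section 17.2 opens with "Participation in the study and study specific therapy must be stopped at any time during the study in individual patients" and gives four reasons: withdrawal of consent, severe toxicity, intercurrent disease and "progression of disease". The toxicity and intercurrent-disease reasons are tied to limits on giving therapy. The progression reason has no such qualifier.

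Other parts of the protocol ask for data that run past progression:

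- Section 11.4: "Protocol visits are required at registration for the trial and at end of radiotherapy and at 1,3 and 6 months after end of treatment". No exception is made for progression. The same list has "Quality of life (EORTC-QLQ C30) (only at 6 months", so there is one quality-of-life value after baseline.
- Synopsis: the secondary endpoints include "Overall survival" and quality of life, and follow-up is at least 6 months.
- Section 14: the adjudication committee receives scans for every patient until the trial ends.
- Appendix 4 (flowchart): survival, VAS, toxicity and AE/SAE are marked at each visit to month 6.

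On treatment length, section 10.3 says "All four fractions of the treatment should be given within two weeks of starting the radiotherapy". On imaging, section 10.1 says that additional MRI "will be performed at 1 and 6 months after end of radiotherapy or in case of progression of the dominant symptom", and section 11.5 says the same in substance.

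**The concern.** A site with a patient who progresses at month 2 cannot follow both section 17.2 and section 11.4. The first ends the patient's participation; the second requires visits at months 3 and 6. No section provides for follow-up after the stop.

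If section 17.2 is applied as written, the 6-month quality-of-life and VAS values come mainly from patients who are alive and have no known progression. In a palliative trial that is a selection towards better outcomes. A patient who leaves for progression before month 6 has no quality-of-life value after baseline. Survival, toxicity and AE/SAE information after progression is not collected. Local symptom progression-free survival (section 10.1) is cut short when exit is due to progression elsewhere.

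This is a question of which data are recorded, so an analysis plan cannot repair it afterwards. Three sites in two countries could also apply the clause differently.

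**Working it through.** The protocol gives no figure of its own on this point, so there is nothing to reproduce. The conflict is established from the text. The arithmetic only illustrates its possible size.

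**Step 1: the texts side by side**

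| Item | Asked for elsewhere | Effect of section 17.2 read literally |
|---|---|---|
| Visits at 1, 3, 6 months (11.4) | All patients, no exception | End at progression |
| Quality of life (11.4, flowchart) | Baseline and month 6 only | No post-baseline value after earlier exit |
| VAS, toxicity, AE/SAE (11.3, 11.4, flowchart) | End of radiotherapy and each visit to month 6 | Only values before exit |
| Overall survival (Synopsis, flowchart) | To month 6 at least | Deaths after exit not collected |
| Scans to the adjudication committee (14) | All patients to end of trial | End at progression |
| MRI for ADC (10.1, 11.5) | Months 1 and 6, or at progression of the dominant symptom | Partly covered by the scan at progression |
| Radiotherapy completion (primary) | Four fractions, two weeks | Essentially none |
| Progression-free survival | To progression | None where exit is its own event |

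**Step 2: what the rule can still stop**

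Once the four fractions have been given, no study therapy remains. For progression after that point the clause acts on data collection alone.

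**Step 3: illustrative size**

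- From the protocol: N = 34 (section 16.1) and expected median survival 3 to 12 months (section 6).
- Assumed: median survival 7.5 months, the middle of that range; median time to progression T of 2 to 12 months; death hazard h before progression and r·h after it, with r from 1 to 2; constant hazards; exit at the moment of progression; time counted from the end of radiotherapy.

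With l = ln 2 / T:

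- Alive and unprogressed at 6 months: exp(−6(l + h))
- Alive at 6 months: exp(−6(l + h)) + l·[exp(−6rh) − exp(−6(l + h))] / (l + h − rh)
- h is solved so that median survival is 7.5 months. At r = 1, h = ln 2 / 7.5 = 0.0924.

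| T (months) | r | l | h | Alive of 34 | Alive and unprogressed of 34 |
|---|---|---|---|---|---|
| 2 | 1 | 0.3466 | 0.0924 | 34 × 0.574 = 19.5 | 34 × exp(−2.634) = 2.4 |
| 4 | 2 | 0.1733 | 0.0656 | 34 × 0.587 = 20.0 | 34 × exp(−1.433) = 8.1 |
| 6 | 2 | 0.1155 | 0.0712 | 34 × 0.585 = 19.9 | 34 × exp(−1.120) = 11.1 |
| 12 | 2 | 0.0578 | 0.0795 | 34 × 0.582 = 19.8 | 34 × exp(−0.824) = 14.9 |

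So about 20 of 34 are alive at month 6. Of these about 2 to 15 are unprogressed, or 2 to 11 if T is limited to 2 to 6 months.

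**Step 4: relaxing immediate exit**

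No visit is scheduled between months 3 and 6. If progression in that interval is found only at the month-6 visit, quality of life and VAS can still be taken there. The relevant count is then patients unprogressed at month 3 and alive at month 6: exp(−3(l + h)) × S(3), where S(3) is the alive formula with 3 in place of 6.

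- T = 2, r = 1: 34 × 0.268 × 0.758 = 6.9
- T = 12, r = 2: 34 × 0.662 × 0.774 = 17.4

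That gives about 7 to 17 of 34. It is a favourable bound, since symptomatic progression may be reported between visits.

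**The case against.** The strongest reply is that a visit schedule always presupposes that the patient is still in the study, so section 17.2 is simply the exception to section 11.4. A therapy-only intent is also plausible. Two of the four reasons concern giving therapy, MRI is requested at symptom progression, the adjudication committee is to see scans from all patients, and minimum follow-up is 6 months. This stands as evidence of intent. It does not remove the problem: the sentence names participation separately from therapy, and the passages that suggest the softer intent are the ones section 17.2 contradicts.

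It is also fair that progression is undefined in section 17.2, while the protocol elsewhere uses symptom progression, local symptom progression-free survival and progression-free survival. How often the rule would apply is therefore unknown, and any count is an illustration.

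A reader might infer that overall survival is necessarily biased upwards by a calculable amount. The documents do not support that. They do not say that survival is censored at exit, and such a rule may properly sit in an analysis plan that is not shown. They give neither a progression rate nor post-progression mortality, and with equal hazards before and after progression the bias is zero.

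Finally, VAS and toxicity are also recorded at the end of radiotherapy and at months 1 and 3, so only the values after exit are at risk, and deaths thin the month-6 data whatever section 17.2 says.

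**Conclusion.** The inconsistency is real in the current text and rests on no assumption. Section 17.2 ends participation at an undefined progression event, at any time, while other sections require data to month 6 and make no provision for follow-up after the stop. Month-6 quality of life is hit hardest, because it is the only post-baseline value. VAS, toxicity, AE/SAE and survival data after progression are also exposed.

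The size is illustrative. Under the stated assumptions about 20 of 34 patients are alive at month 6, of whom about 2 to 15 are unprogressed. More would contribute if progression is first found at the month-6 visit. Overall survival would be informatively censored only if it is censored at exit and mortality is higher after progression; no bias figure is claimed.

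It would go too far to infer that the feasibility result is undermined or that the 6-month ADC endpoint is lost. The primary endpoint is settled over a two-week course, progression-free survival is unaffected where exit is its own event, and MRI at progression of the dominant symptom partly covers ADC. The point concerns secondary endpoints and should be corrected.

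**What to change.** Reconcile section 17.2 with the Synopsis, sections 10.1, 11.4, 11.5 and 14, and the flowchart by separating two events:

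- **End of study therapy:** the listed reasons stay unchanged. No view is taken here on when treatment should stop.
- **End of follow-up:** state that the visits already scheduled, AE/SAE collection and survival status continue to 6 months or death unless the patient withdraws consent to follow-up, with MRI as section 11.5 already provides.

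The cost is a short amendment that adds no visit. The downside is some follow-up effort for patients who have progressed, in a population that section 3 describes as typically frail.
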